7.2 Determination of sample size

7.2.1 Part A Dose escalation, expansion and food effect cohort

In Part A, all patients dosed with DZD9008 will be included. The total number of patients will depend upon the number of dose escalation necessary. It is anticipated that there will be approximately 5 escalation cohorts, hence approximately 30 evaluable patients will be included for escalation.

To better evaluate the safety and anti-tumor efficacy to help define the RP2D, approximately 90 - 110 patients will be enrolled into 6 different expansion cohorts of Part A to explore safety,

[figure not shown]
Date: July 24,2023

PK and efficacy of DZD9008 under fasted or low-fat meal condition at 200 mg and 300 mg dose level, respectively. In addition, a separated cohort of 10 patients will be recruited to evaluate food effect on the PK.

7.2.2 Part B Dose extension cohort

In Part B, subjects will be randomized into one of the two dose cohorts. Each dose cohort uses a Simon two-stage design.

Considering there are two dose cohorts in the pivotal study and the primary endpoint will be analyzed within each cohort independently, Bonferroni method is employed to control the family-wise type I error (at one-sided 0.025). The analysis in two cohorts will be performed independently, at one-sided significance level of 0.0125.

7.3 Calculation or derivation of safety variables

Safety and tolerability will be assessed in terms of AEs, SAEs, laboratory data, vital signs, ECG changes. These will be collected for all patients. Appropriate summaries of these data will be presented as described in Section 7.8.

ECG Changes

Immediate clinical management of patients will be according to local assessment of the QT interval. For the Clinical Study Report QTc will be calculated using Fridericia's or Bazett's formulae.

Creatinine Clearance

Estimated creatinine clearance will be calculated using the Cockcroft and Gault formula;

For creatinine values in mol/L

Men: $[(140 - age) \times weight (kg) \times 1.23] / creatinine (\mu mol/L)$

Women: $[(140 - age) \times weight (kg) \times 1.04] / creatinine (\mu mol/L)$

For creatinine values in mg/dL

Men: $[(140 - age) \times weight (kg)] / (creatinine \times 72)$

Women: $[(140 - age) \times weight (kg) \times 0.85] / (creatinine \times 72)$

Date: July 24,2023

Or others per local practice.

Other significant adverse events

During the evaluation of the AE data, in addition to CRO medical monitor, a Dizal medically qualified or designated expert or designated will review the list of AEs that were not reported as SAEs and AEs leading to discontinuation of investigational product. Based on the expert's judgement, adverse events of particular clinical importance may, after consultation with the Study Physician, be considered other significant adverse events (OAEs) and reported as such in the Clinical Study Report. A similar review of laboratory values, vital signs, ECGs and other safety assessments will be performed for identification of other significant adverse events.

Examples of these are marked hematological and other laboratory abnormalities, and certain events that lead to intervention (other than those already classified as serious), dose reduction or significant additional treatment.

7.4 Calculation or derivation of pharmacokinetic variables

The actual sampling times will be used in the parameter calculations and PK parameters will be derived using standard non-compartmental methods.

Where possible the following PK parameters will be determined for DZD9008.

Following the single dose part (or first dose) of the study:

Maximum plasma concentration (C_{max}), time to C_{max} (t_{max}), terminal rate constant (λz), terminal half-life ($t_{1/2}\lambda z$), area under the plasma concentration-time curve from zero to 24 hours ($AUC_{(0-24)}$), area under the plasma concentration-time curve from zero to 168 hours ($AUC_{(0-168)}$), from zero to the time of the last measurable concentration ($AUC_{(0-t)}$) and from zero to infinity ($AUC_{(0-t)}$), apparent plasma clearance (CL/F), apparent volume of distribution (V_{ss}/F), mean residence time (MRT), as well as the regression based diagnostic parameters (λz Interval, λzN , Rsq adj, λz period/ $t_{1/2}\lambda z$, tlast, AUC_{extr}).

For Part A dose expansion and Part B dose extension, maximum plasma concentration (C_{max}), time to C_{max} (t_{max}), area under the plasma concentration-time curve from zero to 24 hours ($AUC_{(0-24)}$).

Following the multiple dose part of the study:

Maximum plasma concentration at steady state ($C_{ss,max}$), time to $C_{ss,max}$ ($t_{ss,max}$), minimum plasma concentration at steady state ($C_{ss,min}$), area under the plasma concentration-time curve from zero to the end of the dosing interval (AUC_{ss}), apparent plasma clearance at steady state (CL_{ss}/F), extent of accumulation on multiple dosing for AUC and C_{max} (RAC(AUC) and RAC (C_{max})), time dependency of the pharmacokinetics, and urinary PK parameters: amount excreted (Ae) [by collection interval and cumulatively over the collection intervals], percentage of the dose excreted unchanged in urine (Fe [%]) [by collection interval and cumulatively over the collection intervals] and urinary clearance (CL_R).

The maximum plasma concentration (C_{max}), the C_{max} at steady state ($C_{ss,max}$), the time of maximum concentration (t_{max}) and the t_{max} at steady state ($t_{ss\ max}$) will be determined by

Date: July 24,2023

inspection of the concentration-time profiles. Where possible the λz will be calculated by log-linear regression of the terminal portion of the concentration-time profiles where there are sufficient data and the $t_{1/2}\lambda z$ will be calculated as $\ln 2/\lambda z$. All AUC $_{(0-t)}$ values ((AUC $_{(0-t)}$, AUC $_{(0-24)}$, AUC $_{(0-168)}$, AUC $_{(0-168)}$, AUC $_{(0-t)}$) will be calculated using the linear up/log down rule. Where appropriate, the AUC $_{(0-t)}$ will be extrapolated to infinity using λz to obtain AUC $_{(0-\infty)}$. The CL/F following the single dose and CL $_{ss}$ /F following multiple dosing will be determined from the ratio of dose/AUC $_{(0-\infty)}$ and dose/AUC $_{ss}$, respectively. The volume of distribution (V $_{ss}$ /F) will be determined from the mean residence time (MRT) x CL/F. The RAC will be calculated as the ratio of the AUC $_{ss}$ or C $_{max}$ on Cycle 2 Day 1 and AUC $_{(0-24)}$ or C $_{max}$ on Cycle 0 Day 1. The time dependency of the pharmacokinetics on multiple dosing will be assessed by the calculation of the ratio of AUC $_{ss}$ on Cycle 2 Day 1/AUC $_{(0-\infty)}$ on Cycle 0 Day 1.

The equation for calculating the amount excreted in the urine is: Ae (µmol or ng) = urine volume (mL) * concentration (µmol/mL or ng/mL). The weight/volume of urine and the concentration of drug in urine are usually recorded assuming that 1 g corresponds to 1 mL of urine. Urine concentrations below LLOQ will be treated as numerical zero. The percentage of dose excreted unchanged in the urine (e.g. Fe [%]) will be calculated by dividing the corresponding Ae in the collection period by the dose administered and multiplying by 100.

Renal clearance can be calculated by:. CL_R (L/h) = Ae_{0-t} (μ mol or ng) / AUC_{0-t} (μ mol.h/L or ng.h/L) where the 0-t interval is the same for both Ae and AUC.

Where possible the appropriate pharmacokinetic parameters will also be determined for the metabolites of DZD9008.

Additional PK parameters may be derived where appropriate.

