5. STUDY TREATMENT AND CONDUCT

5.1 Treatment

Supply, Packaging and Labeling of DZD9008

DZD9008 drug substance and drug product to be used for this clinical study are manufactured in accordance with Good Manufacturing Practice (GMP).

DZD9008 will be supplied by Dizal as 25 mg, 50 mg, 100 mg, 150 mg and 200 mg tablet by IRT system.

Labels will be prepared in accordance with GMP and local regulatory guidelines. The labels will fulfil GMP requirements for labelling. Label text will be translated into local language.

The label will include the Name of the Sponsor, Study Code, for clinical trial use only and /or any other specific requirements.

DZD9008 tablets of 25 mg, 50 mg, and 100 mg strengths are presented as yellow, round shaped, biconvex, and film-coated tablets. Each HDPE bottle contains 25 units of one strength of the above mentioned 3 different tablets, and with 1 g of pre-packed silica-gel. DZD9008 tablets of 150 mg and 200 mg strengths are presented as yellow, caplet shaped ,biconvex ,and film-coated tablets, with debossing of either the "150 mg" or "200 mg" on one side and the company logo on the other side. The tablet core is off-white to pale yellow after removing the coating film. Each HDPE bottle contains 30 units of one strength of the mentioned 150 mg or 200 mg tablets, and with 1 g of pre-packed silica-gel.

DZD9008 tablet must be stored at storage condition of up to 30 °C in the original container(s). The stability study of DZD9008 clinical batches is on-going and will be continued to at least cover the whole clinical trial. The shelf life will be evaluated when stability data becomes available.

All study drugs should be kept in a secure place under appropriate storage conditions. The investigational product label specifies the appropriate storage condition.

Date: July 24,2023

Drug administration

DZD9008 will be given orally, once daily except for Cycle 0 in Part A dose escalation and food effect cohort.

In Part A dose escalation cohort and dose expansion cohorts 1 and 2, patients are required to keep a fasted condition for \geq 1 hour prior to and \geq 2 hours post dosing. Water is permitted during this fasted period.

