- Higher incidence of dose reduction and interruption occurred at 400 mg cohort was observed as compared to 200 mg and 300 mg cohort, which presumably led to lower clinical efficacy at the 400 mg cohort (ORR 25% at 400 mg). As the doses of 100 mg or above demonstrated clinical activity, and 200 mg or 300 mg is expected to overcome PK variability of DZD9008 to achieve pharmacological relevant exposure required from different subtypes of Exon20ins, thus selecting both 200 mg and 300 mg is appropriate to further evaluate DZD9008 dose optimization for the phase 2 pivotal study.
- DZD9008 elimination half-life is approximately 50 hours following a single dose across the doses investigated, which supports the once daily dosing regimen of DZD9008 in clinical development.

Ethnic sensitivity

 Based on the available data, no obvious difference in safety, PK and anti-tumor efficacy of DZD9008 was observed between Asian and White patients across different regions/countries. Therefore, Dizal believes that the use of same dose and schedule across different regions and countries is appropriate.

Patients enrolled to Part B will receive repeated dosing of DZD9008 at 200 mg or 300 mg once daily. Following review and approval form IEC/IRB and/or local regulatory authority (as applicable) on the optimal RP2D selction, eligible patients can be enrolled into the optimal RP2D cohort. The ongoing patients previously randomized to the suboptimal Part B dose cohort can maintain the same dose level, or shift to receive the optimal RP2D, if judged by the investigator that it is of the best clinical benefit to patients and re-consent is needed (see section 5.1). DZD9008 will be administrated with food as dosing with high fat food in Part A showed limited effect on DZD9008 exposure. Patients with prior therapy may be stratified into subcohorts when data is analyzed.

Patients will receive repeated daily dosing of DZD9008 until disease progression, intolerable AEs, discontinuation criteria have met or withdrawal of consent.

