6.5.1.1 Part A (Dose escalation)

Blood samples

Venous blood samples will be taken at the time points shown Table 5. Discussion with the Clinical Pharmacologist from Dizal Pharmaceuticals is required as to any impact if dose interruption occurs within 3 days of scheduled time points for PK sampling. The date and time of dosing and collection of each sample will be recorded.

Time points on Cycle 0 Day 1 are pre-dose, 0.5, 1, 2, 3, 4, 6, 8, 10, 12, 24, 48, 72, 120 and 168 hours post-dose.

Time points on Cycle 2 Day 1 are pre-dose, 0.5, 1, 2, 3, 4, 6, 8, 10, 12 and 24 hours post-dose. On Cycle 1 Day 1, Day 8, Day 15, and Cycle 3, 4, 5 Day 1, pre-dose samples are collected.

The timing for PK sampling may be adjusted with emerging data during the study, in order to ensure appropriate characterization of the plasma concentration-time profiles of DZD9008 (Table 5).

Hospitalization can be allowed for out of business time PK collection.

Blood samples (approximately 4 mL at each time point) will be collected and put into lavender top (EDTA) Vacutainer[®] evacuated collection tubes at the time points indicated. After processing, plasma samples will be split, for quantification of DZD9008 and identification and semi-quantification of all possible metabolites. The timing for PK sampling may be adjusted with emerging data during the study, in order to ensure appropriate characterization of the plasma concentration-time profiles of DZD9008.

Urine samples

Urine samples (approximately 5 mL) for the determination of concentrations of DZD9008 and characterization of its metabolites will be taken from the total urine samples provided during 0-24 h at Cycle 2 Day 1. The date and time of collection and the weight of each urine collection will be recorded. Samples will be split into aliquots, for quantification of DZD9008 and for identification and semi-quantification of all possible metabolites.

The interval for urine collection on Cycle 2 Day 1 are 0 - 4, 4 - 12, and 12 - 24 hours. The timing for PK sampling may be adjusted with emerging data during the study, in order to ensure appropriate characterization of urine excretion DZD9008.

In addition, the pharmacokinetic samples may be subjected to further analyze by Dizal Pharmaceuticals or CROs in order to investigate the presence and/or identity of additional drug metabolites. Any results from such analyses will be reported separately from the Clinical Study Report.

Food effect

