Scatter plots of PK parameters versus dose, or log-dose will also be considered following both single (escalation only) and multiple dose administration of DZD9008 to assess dose proportionality in Part A.

In a preliminary assessment of dose proportionality, log-transformed $AUC_{(0-\infty)}$ and/or $AUC_{(0-t)}$ and C_{max} parameter estimates will be examined using the Power Model:

```
parameter = e^a (dose)b
i.e., log(parameter) = a + (b * log(dose))
```

where a is the intercept, depending on patients, and b is the slope, measuring the extent of dose proportionality. Dose proportionality implies that b=1 and will be assessed by estimating b along with its confidence interval.

If there is evidence of departures from dose proportionality, log-transformed dose-normalized AUC and C_{max} of DZD9008 will be analysed separately using a mixed effects model. Dose will be fitted as a fixed effect and patient as a random effect. Point estimates and associated 90% confidence intervals (CIs) for the differences between each dose level and the reference dose (the lowest dose) will be constructed using the residual variance. The estimates will then be back-transformed to provide point estimates and corresponding 90% CIs for the ratios of each dose level to the reference dose on the original scale. No adjustments for pre-planned multiple comparisons will be made. This analysis will only be performed provided there are sufficient data.

If there are more than 20% patients whose $AUC_{(0-\infty)}$ values are not calculable for either treatment due to large extrapolated area (> 20%), Rsq adjusted <0.80 or any other reason, $AUC_{(0-t)}$ will also be analyzed statistically and presented in the same way as $AUC_{(0-\infty)}$. Otherwise, $AUC_{(0-t)}$ will not be statistically analyzed.

The same analysis will be performed on AUC_{ss} and C_{ss,max} from Cycle 2 Day 1 PK data.

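### Protocol 7.4 labels MRT × CL/F after an oral dose as Vss/F, although oral MRT includes absorption time; the upward bias is small and confined to descriptive Part A pharmacokinetics

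*Protocol*

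**What the plan says.** Dosing is oral in every cohort. Protocol 5.1 (Drug administration) states: "DZD9008 will be given orally, once daily except for Cycle 0 in Part A dose escalation and food effect cohort". No part of the study gives the drug intravenously.

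Protocol 7.4 says that "PK parameters will be derived using standard non-compartmental methods". For the single-dose part it lists MRT and Vss/F among the parameters but does not define MRT: there is no AUMC formula, no statement of 0 to t or 0 to infinity, and no absorption term. CL/F after the single dose is dose/AUC(0-∞), where the measured area "will be extrapolated to infinity using λz to obtain AUC" to infinity. Vss/F then "will be determined from the mean residence time (MRT) x CL/F".

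Protocol 7.9.4 summarises Vss/F with CL/F and other parameters, using arithmetic mean, standard deviation, minimum, maximum and number of observations. For Part A expansion and Part B, section 7.4 limits the first-dose parameters to Cmax, tmax and AUC(0-24), so Vss/F arises only from the Part A single-dose data. Tables 3 and 4 of the Part B SAP list neither MRT nor Vss/F.

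**The concern.** MRT × CL = Vss is an intravenous-bolus identity. After an oral dose, the MRT taken from the plasma profile is the intravenous MRT plus MAT. The formula in 7.4 therefore returns

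MRT(oral) × CL/F = Vss/F + MAT × CL/F.

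The extra term cannot be negative. It cannot be removed non-compartmentally without an intravenous reference, and the general appeal to standard non-compartmental methods does not remove it, because 7.4 prescribes the product explicitly.

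What is at stake is the label on a reported number. Characterising the pharmacokinetics is a Part A secondary objective (Protocol 1.1.1.2). A volume computed this way moves with absorption rate as well as with distribution. In the food-effect cohort, which takes single doses fed and fasted, it could differ between conditions even if distribution did not.

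**Working it through.** The documents give no value for MRT, AUMC or Vss/F, so there is no figure to reproduce. The check sizes the absorption term and then compares the two candidate volumes.

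**Inputs**

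- Half-life 50 h. Protocol 5.1.4: "DZD9008 elimination half-life is approximately 50 hours following a single dose across the doses investigated".
- Last single-dose sample at T = 168 h. Protocol 6.5.1.1: "24, 48, 72, 120 and 168 hours post-dose".
- tmax: the value in Protocol 2.3.5 is missing from the public text. Assumed range 2 to 12 h.
- Model: one compartment with first-order absorption (assumption). MRT is read as 0 to infinity, to match CL/F.

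**Size of the absorption term**

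- k = ln 2/50 = 0.01386 per h, so intravenous MRT = 1/k = 72.1 h.
- ka is solved from tmax = ln(ka/k)/(ka − k), and MAT = 1/ka.
- Relative bias in Vss/F = MAT/(1/k) = k × MAT.

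| Assumed tmax (h) | ka (per h) | MAT (h) | Bias in Vss/F |
|---|---|---|---|
| 2 | 2.638 | 0.38 | +0.5% |
| 4 | 1.109 | 0.90 | +1.2% |
| 6 | 0.657 | 1.52 | +2.1% |
| 8 | 0.448 | 2.23 | +3.1% |
| 10 | 0.331 | 3.02 | +4.2% |
| 12 | 0.257 | 3.89 | +5.4% |

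**Extrapolated share beyond 168 h**

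- kT = 0.01386 × 168 = 2.329.
- AUC: exp(−2.329) = 9.7%.
- AUMC: (1 + 2.329) × exp(−2.329) = 32.4%.

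**Sensitivity to an error in λz** (true half-life 50 h, tail beyond 168 h extrapolated with the wrong λz, absorption ignored)

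| Error in λz | MRT × CL/F | Vz/F = dose/(λz × AUC(0-∞)) |
|---|---|---|
| −20% | +5.9% | +22.0% |
| +20% | −3.7% | −15.3% |

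MRT × CL/F equals dose × AUMC/AUC², so errors in the two tails partly cancel. Vz/F has λz directly in its denominator, so they do not. In the one-compartment model Vz/F has no absorption bias.

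**The case against.** Four points can be made on the other side.

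- **Nothing turns on it.** Dose proportionality (7.9.4) and the food effect (7.9.5) are analysed on AUC and Cmax. No stated escalation rule, sample size or Part B analysis uses Vss/F. This stands and sets the weight of the point.
- **MRT is undefined, so the direction is not certain.** If MRT were truncated at 168 h, Vss/F would be about 21% to 25% too low at a 50 h half-life. The 0-to-infinity reading is the consistent one, because the CL/F it multiplies uses AUC(0-∞). The objection is a further reason to define MRT; it does not rescue the formula.
- **Vz/F is a different parameter.** It equals Vss/F in the one-compartment model and exceeds it in a multi-compartment one. Section 7.4 also already allows additional parameters. Both are true, but adding Vz/F would still leave a quantity reported under the name Vss/F that is not Vss/F.
- **The operative rules may be elsewhere.** SAP section 1 says the Part A analyses are in a separate plan, which is not available here and may already deal with this. The protocol text would still need to agree with it.

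A reader might infer from the 32% extrapolated share of AUMC that Vss/F is less precise than Vz/F, or that extrapolation is what pushes it upward. Neither follows. The λz comparison runs the other way, and extrapolation adds imprecision rather than upward bias. Nor is extrapolation unguarded: 7.9.4 treats AUC(0-∞) with more than 20% extrapolated as not calculable, and CL/F, hence Vss/F, depends on AUC(0-∞).

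**Conclusion.** The formula is wrong for an oral dose and should be corrected, as a minor point. On the 0-to-infinity reading the reported value overstates Vss/F by roughly 0.5% to 5%. That range rests on the assumed tmax of 2 to 12 h, the stated half-life of about 50 h and a one-compartment model. With more than one compartment the intravenous MRT is shorter than 1/λz, so the same MAT would give a somewhat larger relative bias.

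A reader might infer a larger problem, and the documents do not support it. A bias of about 11% needs MAT of 8 h, which in this model means a tmax near 20 h; no reported value supports that. An extrapolated AUMC share of about one half needs a half-life near 70 h, against the 50 h the protocol gives across doses. The effect is limited to descriptive Part A single-dose pharmacokinetics.

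**What to change.** In Protocol 7.4 and 7.9.4, and in the separate Part A analysis plan:

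- report Vz/F = dose/(λz × AUC(0-∞)) as the apparent volume after the single oral dose;
- define MRT as 0 to infinity and label it as including absorption time;
- do not present MRT × CL/F as Vss/F.

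The cost is wording. λz and AUC(0-∞) are already derived, and no new samples are needed. The downside is the sensitivity to λz shown above, so Vz/F should be read beside the λz diagnostics that 7.9.4 already lists, and should not be described as an estimate of Vss/F.

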7.5 Calculation or derivation of tumor response variables

Independent Central Review of RECIST based assessments

The Independent Review Committee (IRC) will review all the images collected from Part B of the study and images collected from patients with EGFR Exon20ins in Part A of the study when needed. IRC review of all radiological imaging data will be carried out using RECIST version 1.1. All radiological scans for all patients (including those at unscheduled visits, or outside visit windows) will be provided to the IRC. Prior radiotherapy reports for patients (at baseline) and information on biopsied lesions will also be provided to the IRC to allow the selection of appropriate target lesions. The imaging scans will be reviewed by two independent radiologists using RECIST 1.1 criteria and will be adjudicated if required. For each patient, the IRC will define the overall visit response data (CR, PR, SD, PD or NE) and the relevant scan dates for each time point (i.e. for visits where response or progression is/is not identified). If a patient has had a tumor assessment which cannot be evaluated then the patient will be assigned a visit response of not evaluable (NE) (unless there is evidence of progression in which case the response will be assigned as PD). Endpoints (ORR, DoR, DCR, PFS) will be derived from the scan dates. ORR will only include patients whose response has been confirmed by a second scan at least 4 weeks after the initial response. The endpoint of tumor shrinkage will be assessed from tumor size measurements based on the primary independent radiologist assessment.

Date: July 24,2023

Results from the independent review will not be communicated to investigators. The management of patients will be based solely on the results of the RECIST 1.1 assessment conducted by the investigator.

For more detailed information refers to recent IRC charter.

Investigator RECIST based assessments

From the investigators review of the imaging scans, the RECIST tumor response data will be used to determine each subject's visit response according to RECIST version 1.1. At each visit, patients will be assigned a RECIST 1.1 visit response of CR, PR, SD or PD depending on the status of their disease compared with baseline and previous assessments.

Progression of TLs will be calculated in comparison to when the tumor burden was at a minimum (i.e., smallest sum of diameters previously recorded on study). In the absence of progression, tumor response (CR, PR, SD) will be calculated in comparison to the baseline tumor measurements obtained before starting treatment.

If a patient has had a tumor assessment, which cannot be evaluated, then the patient will be assigned a visit response of not evaluable (NE) unless there is evidence of progression in which case the response will be assigned as PD.

• A visit response of CR will not be allowed if any of the TL data is missing

